The CDC's initial interim guidelines for dental settings during COVID-19 suggested that using a pre-procedural rinse with an antimicrobial product (such as chlorhexidine gluconate, essential oils, hydrogen peroxide, povidone-iodine, or cetylpyridinium chloride) could have a potential effect in reducing the level of oral microorganisms in aerosols and spatter generated during dental procedures⁷. In April 2020, the CDC and the American Dental Association (ADA) recommended using a mouthwash containing 1.0-1.5% H₂O₂ as a pre-procedural rinse before dental treatment to reduce SARS-CoV-2 load potentially; however, no US clinical studies have been conducted to support this claim.

This study aims to assess the effect of four over-the-counter (OTC) antiseptic mouthwash/gargling solutions compared to a distilled water control on the SARS-CoV-2 load in unstimulated saliva, throat wash (gargle lavage), and oropharyngeal swab samples. Also, study participants will be assessed for the severity of their clinical symptoms during the study period. The 4-week protocol was selected as studies show people with COVID can continue to shed the virus and potentially transmit to the others for a 2- to 4-week period. This study will also examine tobacco use, marijuana smoking, or vaping as possible effect modifiers of antiseptic mouthwash on SARS-CoV-2. Study participants will be followed up daily via a very short daily questionnaire and every 3 months for the next 11 months after the study is finished for longerterm follow-up via text messaging. The null hypothesis of the study is that there is no difference between any OTC antiseptic mouthwash solution (Chlorine Dioxide (ClO₂), Hydrogen Peroxide (H₂O₂), Cetylprydinium Chloride (CPC), Essential Oils (EO), and distilled water (H₂O) in reducing SARS-CoV-2 load in unstimulated saliva, throat wash (gargle lavage), and oropharyngeal swab samples (baseline to 4 week follow-up).

Objectives {7}

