1a. To assess and compare the SARS-CoV-2 viral load in unstimulated saliva and throat wash (gargle lavage) samples before and after rinse at baseline in Chlorine Dioxide (ClO₂), Hydrogen Peroxide (H₂O₂), Cetylprydinium Chloride (CPC), and Essential Oils (EO) groups versus distilled water (H₂O) group (pre-procedural rinse primary outcome measure).1b. To assess the SARS-CoV-2 viral load reduction of throat wash (gargle lavage) samples from baseline to 4 weeks in Chlorine Dioxide (ClO₂), Hydrogen Peroxide (H₂O₂), Cetylprydinium Chloride (CPC), and Essential Oils (EO) groups versus distilled water (H₂O) group solution of throat wash (gargle lavage) samples from baseline to 4 weeks in Chlorine Dioxide (ClO₂), Hydrogen Peroxide (H₂O₂), Cetylprydinium Chloride (CPC), and Essential Oils (EO) groups versus distilled water (H₂O) group (homecare reduction primary outcome measure).

2. To assess the clinical symptom onset progression and health care utilization (e.g. hospitalization) from baseline to 4 weeks comparing Chlorine Dioxide (ClO₂), Hydrogen Peroxide (H₂O₂), Cetylprydinium Chloride (CPC), Essential Oils (EO) to distilled water (secondary outcome measures).

3. To assess if tobacco use, marijuana smoking, or vaping are effect modifiers of primary outcome measures.

4. To evaluate study participants' in a 12-month follow up.

Trial design {8}

This is a single center, 5-arm, parallel groups, double-blinded (participant, outcomes assessor),

randomized controlled trial of adults who are COVID-19 positive using over-the-counter (OTC) mouthwash/gargling solutions: Chlorine Dioxide (ClO₂) (CloSYS Ultra Sensitive, Rowpar Pharmaceutical Inc., USA); Hydrogen Peroxide (H₂O₂) (Oral-B Mouth Sore, Proctor & Gamble, USA); Cetylprydinium Chloride (CPC) (Crest Pro-Health Multi-Protection, Proctor & Gamble, USA); Essential Oils (EO) (Listerine Zero, Johnson & Johnson, USA) versus distilled water as a control.

Methods: Participants, interventions and outcomes

Study setting {9}

Consenting community-dwelling San Francisco Bay Area (California, USA) participants positive for COVID-19.

Eligibility criteria {10}

Inclusion criteria

- Adults 18 years and older
- Tested positive for COVID-19 with a sample collected in the prior 7 days
- Ability to read and speak in English or Spanish
- Ability to participate in the study for 4 weeks
- Ability to gargle
- Not having any oral condition that might worsen with gargling solutions

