 - Change in self-reported (questionnaire) clinical symptom onset in tobacco users, marijuana smokers, or vapers. A symptom checklist will include: cough, runny nose, scratchy/sore throat, fever, chills, fatigue, muscle ache, shortness of breath, diarrhea/nausea/vomiting, loss of taste/smell, and red /painful eye (Time Frame: Baseline to 4 weeks)
 - Change in healthcare utilization and hospitalization in tobacco users, marijuana smokers, or vapers (Time Frame: Baseline to 4 weeks)

Participant timeline {13}

Study participants will remain in the trial for 4 weeks. After completing the intervention, they will be followed up for the next 11 months via text messaging to ask about clinical symptoms and healthcare utilization, experience using mouthwash, and their interest in using mouthwash after the trial.

Sample size {14}

A total of 150 eligible individuals will be enrolled in the trial after providing informed consent and randomly assigned to 1 of 5 groups. This trial is sized to provide precise estimates of effect size for a future definitive trial with at-risk individuals. However, this trial would be able to detect a rather large effect: a sample size of 24 for a mouthwash group and 24 for the distilled water control group is estimated to have 80% power to detect a 2-fold difference in mean values between the 2 groups with a 2-sided alpha=0.05. Assuming 80% retention through 28 days, 30 participants per group at baseline (150 total) will be enrolled.

Recruitment {15}

Two recruitment routes have been planned for this trial:

1- Upon referring to testing centers at UCSF individuals will receive the trial details via a letter or flyer, and if tested positive for COVID-19, they will contact study staff and enroll into the trial.

2- The UCSF Clinical and Translational Science Institute (CTSI) Participant Recruitment Program (PRP) provides new COVID+ patient lists enabling us to contact COVID+ patient who are interested in participating in research studies.

After study staff confirm their eligibility, participants will receive the sample collection package and written instructions at their home along with scheduling a videoconference to collect saliva samples and use the assigned mouthwash during the 4-week period.

Assignment of interventions: allocation

Sequence generation {16a}

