At any time during the trial, if a participant discontinues from the study or deviates from intervention protocols, we will record the information.

Data management {19}

We have planned to use unique barcodes on sample collection kits and participants' packages to be scanned during the trial and automatically recorded in an Excel file on a UCSF secured laptop and the Cloud. Only PIs know about the codes. [name] (SB) will supervise data entry and its quality on a regular basis. Data will be linked to a REDCap form.

Confidentiality {27}

Email address and telephone number are the only personal identifying information which will be kept confidential in REDCap on UCSF secured servers. Participant information will be kept confidential. After the study and its follow-up in 12 months is finished, email address and phone number will be deleted.

Plans for collection, laboratory evaluation and storage of biological specimens for genetic or molecular analysis in this trial/future use {33}

The study procedures include collecting saliva and oropharyngeal samples from participants on 3 study days (day 1, 7, 28), assaying them, and storing them for future potential research use.

Statistical methods

Statistical methods for primary and secondary outcomes {20a}

Primary outcome measure: To assess and compare the SARS-CoV-2 viral load in unstimulated saliva and throat wash (gargle lavage) samples at baseline, days 7 and 28, we will compare the viral load (cycle threshold, Ct) among active groups versus the control (water) and within groups on day 28 using proportional hazards regression models with right censoring for undetermined Ct, stratifying on replicate for a marginal repeated measures survival model.

We follow the intention-to-treat (ITT) approach for efficacy analyzing participant data asrandomized; a safety analysis will tabulate any adverse experiences. The ITT group will include participants who are randomized after meeting the eligibility criteria and receive at least one study mouthwash dose and have PCR data from collected samples. A safety analysis group will include participants who received study mouthwashes and have safety evaluation data after using the mouthwash at least once.

Interim analyses {21b}

We plan to conduct an interim analysis after 10 participants in each group (N=50) have finished the 28-day period (using mouthwash). The alpha-spending approach with an O'Brien-Fleming stopping rule will be used.

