Methods for additional analyses (e.g. subgroup analyses) {20b}

Similar proportional hazards regression analyses will be conducted for baseline (after rinse) and day 7. We will assess the relationship between study results and baseline variables (demographics, clinical symptoms, tobacco use, etc.).

Methods in analysis to handle protocol non-adherence and any statistical methods to handle missing data {20c}

Since PCR Ct data (inversely proportional to viral load) are expected to include right censored data when the assay is stopped before sufficient amplified viral genetic material is detected, we plan to use statistical analyses which can accommodate right censoring. Alternatively, we may use multiple imputation for Ct values above the detection level (e.g. 32, 35, or 40) and combine the estimates and variability across multiple imputations.

Plans to give access to the full protocol, participant level-data and statistical code {31c}

We will make the protocol available as per ClinicalTrials.Gov requirements. We do not plan to provide access to participant-level data. We may make statistical code available with publications.

Oversight and monitoring

Composition of the coordinating center and trial steering committee {5d}

SG, study PI and supervisor, and SB, co-PI form the steering committee. They will have regular weekly meetings to review and supervise various study steps and train/lead study staff. They will work with different study staff groups (e.g. recruitment, data management, and lab staff) on a

regular basis to assess trial steps and solve any problems/errors that might rise.

Composition of the data monitoring committee, its role and reporting structure {21a}

SG, the PI, is a biostatistician and clinical trialist who will instruct and supervise study staff on designing questionnaires, data collection, and data analyses. SB, the co-PI, is a dental clinician who will work closely with and report to SG.

Adverse event reporting and harms {22}

REDCap will be configured with Twilio to send a daily text message to participants with a link to a very short REDCap questionnaire asking about previous day mouthwash use and possible adverse experiences.

Frequency and plans for auditing trial conduct {23}

Study PIs will audit trial conduct and trial procedures weekly to resolve possible errors and make decisions about required modifications, staff re-training, etc.

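### The stated 80% power is for fully measured values and does not carry over to the day-28 proportional hazards test, which censors undetermined Ct

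*Combined protocol and SAP*

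**What the plan says.** Sample size {14} gives effect-size estimation for a later trial as the first purpose. It then adds that 24 participants in a mouthwash group and 24 on water are "estimated to have 80% power to detect a 2-fold difference in mean values between the 2 groups with a 2-sided alpha=0.05". It names no test, scale, SD or CV. The step to enrolment is: "Assuming 80% retention through 28 days, 30 participants per group at baseline (150 total) will be enrolled".

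The primary analysis in {20a} compares the active groups with water and "within groups on day 28 using proportional hazards regression models with right censoring for undetermined Ct", stratified on replicate. Section {20c} says that Ct data "are expected to include right censored data when the assay is stopped before sufficient amplified viral genetic material is detected" and offers multiple imputation above the detection level as an alternative that may be used. Section {20b} adds: "Similar proportional hazards regression analyses will be conducted for baseline (after rinse) and day 7".

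Three other passages fix the timing. The background, just before Objectives {7}, justifies the 4-week protocol because "people with COVID can continue to shed the virus and potentially transmit to the others for a 2- to 4-week period". Eligibility {10} requires: "Tested positive for COVID-19 with a sample collected in the prior 7 days". Section {33} places sampling on days 1, 7 and 28.

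Objectives {7} names two primary comparisons: 1a, before and after the rinse at baseline, and 1b, baseline to 4 weeks of home use.

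**The concern.** The power statement concerns a difference in means and counts every retained participant as contributing a value. The day-28 model does not work that way. A participant who stays in the trial but whose Ct is undetermined adds no event, only the information that the Ct lies above the limit. The plan foresees such values in {20c} but makes no allowance for them in {14}, and it tests at a visit at or past the end of its own shedding period.

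The risk lies in interpretation. A null day-28 result for objective 1b could be read as a fair test with 80% power for a 2-fold difference when the test had less. The pilot's first aim is also touched, since the precision of a hazard ratio depends on the number of determined values.

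**Working it through.** **Enrolment.** 24 / 0.80 = 30 per group and 5 × 30 = 150. Both reproduce the plan, and they show that drop-out is the only loss allowed for.

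**What the 80% implies.** It cannot be reproduced directly, because no SD is given. Solving a two-sample t-test (24 per group, two-sided alpha 0.05, power 0.80) gives a standardised effect of 0.826. If one Ct cycle is a 2-fold change, SD = 1 / 0.826 = 1.21 Ct. On the log10 scale this is 0.301 / 0.826 = 0.364. The CV is √(exp((0.693 / 0.826)²) − 1) = 1.01. The t-test would have about 92% power at SD 1.0, 62% at SD 1.5 and 40% at SD 2.

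**Timing.** Day 28 − day 1 = 27 days. Adding 0 to 7 days since the positive sample gives 27 to 34 days, against 14 to 28 days of stated shedding. Day 7 is 6 to 13 days after that sample.

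**Power of the day-28 model.** Assumptions, none of them stated in the plan: the 80% is the log-scale t-test above; the rinse raises Ct by 1 cycle; a common detection limit is set so that a given share of control values is determined. Ct is either normal with SD 1.21 or follows an extreme-value distribution with the same SD, for which hazards are proportional. In the second case the scale is 1.21 × √6 / π = 0.944 and HR = exp(1 / 0.944) = 2.9. The test is the Cox score test with 24 per group, by simulation. Censored values stay in the risk sets, so their information is used. The last column has 1 to 3 replicates with correlation 0.3 to 0.9, scaled so that the participant mean keeps SD 1.21.

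| Control values determined at day 28 | Power, one value per person | Range over 1 to 3 replicates |
|---|---|---|
| 100% | 74–93% | 72–93% |
| 80% | 72–81% | 71–85% |
| 70% | 69–74% | 69–80% |
| 50% | 56–62% | 56–70% |
| 20% | 25–36% | 25–50% |
| 10% | 10–15% | 10–32% |

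Proportional Ct gives the higher figure in the one-value column at 70% and above, and normal Ct at 50% and below. Rejection under no effect was about 4% to 6%. Repeat runs put the top of the one-value range at 20% determined between 36% and 38%. The last column uses a slightly different variance, so its lower ends can be a point or two lower.

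**Check by hand.** Under a constant hazard ratio, power = Φ(√(D/4) × ln HR − 1.96) with D events. Setting this to 80% at D = 48 gives HR = 2.25, ln HR = 0.809. With 50% of all values determined, D = 24 and power = Φ(2.449 × 0.809 − 1.96) = 51%. With 20%, D = 9.6 and power = 24%.

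**Precision.** With normal Ct and 50% of controls determined, the active share is Φ(−0.826) = 0.204, so D = 12.0 + 4.9 = 16.9. With SE(ln HR) ≈ 2/√D, the 95% CI multiplies and divides the HR by exp(1.96 × 2/√48) = 1.76 at 48 events and by exp(1.96 × 2/√16.9) = 2.6 at 16.9.

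**The case against.** - **The determined share is unknown.** The shedding sentence justifies a 4-week protocol. It is not a distribution of RT-PCR results at limits such as 32, 35 or 40. This stands, and it is why the result is given as a range.
- **Little censoring does little harm.** This stands. With 80% of controls determined, some settings still reach 80%. With a smaller SD the model also does better: at SD 1.0 it has 84–85% at 70% determined and 69–76% at 50%.
- **Replicates help.** They do, somewhat. If 1.21 is the SD of a single value and there are three replicates at correlation 0.5, power is 80–85% at 50% determined. The comparison of means would then have 93%, so the stated 80% is still not the power of the planned model.
- **Multiple imputation is available.** It is optional, and imputing above the limit supplies no measurements. The 80% would still describe complete data.
- **This is a pilot, and power is a side remark.** This stands as to weight. The precision calculation shows, however, that estimation is also affected.
- **Objective 1a is primary too.** Correct. It is measured around the rinse at baseline, and the day-28 window does not reach it.

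**Conclusion.** The 80% does not carry over to the day-28 comparison for objective 1b. It belongs to an analysis of mean values with no undetermined results, whereas the planned model censors them and the plan expects them. That {14} counts every retained participant as measured is inferred from 24 / 0.80 = 30 and from the absence of any other allowance. The size of the loss depends on the SD, the determined share, the replicates and the shape of the Ct distribution, none of which is stated.

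Three stronger readings are not supported:

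- A reader might infer that almost nothing will be determined at day 28. Durations uniform on 14 to 28 days would leave (28 − 27) / 14 = 7% still shedding with no lag, and 0.5% averaged over a lag of 0 to 7 days. The plan states neither a uniform duration with hard limits nor that shedding means a determined Ct. Reading 14 to 28 days as a lognormal interquartile range instead gives 27% and 20%.
- A reader might infer that the active arm would have no determined value with probability 77%, so that no hazard ratio could be estimated. That adds a latent normal shift to the 7%. If the rinse left the active share at 7%, the probability would be 0.93^24 = 18%.
- A reader might conclude that the primary test should move to day 7 or to a joint model of both visits. That would change the estimand and give up the formal test at the end of home use. With normal Ct the joint model has only about 75% power, even if day 7 is fully determined and the shift is the same at both visits.

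**What to change.** In {14}, restate the 80% as applying only to an uncensored comparison of mean log viral load, and give the SD or CV behind it. Beside it, report the power or the expected CI width of the {20a} model at day 28 over a stated range of determined shares, with the assumed number of replicates and their correlation. A null day-28 result should then be read against those figures and not against 80%.

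This needs wording and a short calculation. It needs no extra participants or samples and leaves the primary test where it is. The cost is a less favourable stated figure.

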The permuted block allocation sequence stratified on language (English/Spanish) will be generated in SAS and uploaded to REDCap to randomly assign participants to one of the five mouthwash groups.

Concealment mechanism {16b}

The randomization will be concealed in REDCap; once participant's eligibility is confirmed, consent form is signed, and the baseline questionnaire completed, then the assignment is revealed. No study staff involved in recruitment or procedures with participants or participants know the allocation sequence since it is revealed via REDCap after qualifying steps.

Implementation {16c}

Following release of the REDCap allocation sequence for an individual participant, study staff will obtain the relevant kit and deliver to participants.

Assignment of interventions: Blinding

Who will be blinded {17a}

Participants will be blinded/masked to the extent possible by covering product labels, but the solutions have different colors, flavors, and smells so they may guess which group they have been assigned. Lab staff performing assays (outcome assessors) and data analysts will be blinded/masked to intervention group.

Lab staff will receive participants' samples with barcode stickers with only the study ID number. The data analyst will receive data set with coded group identifier.

Procedure for unblinding if needed {17b}

We will not unblind the study groups for outcome assessors unless subsequent actions to assure participants' safety would be affected.

Data collection and management

Data will be collected via various questionnaires (eligibility, baseline, daily and long-term follow ups) designed in REDCap. The data collection will be supervised and assessed regularly for completeness and inconsistencies.

Plans for assessment and collection of outcomes {18a}

We have designed questionnaires (eligibility, baseline, daily and long-term follow ups, sample collection, and RT-PCR results) in REDCap to collect data from participants and assess outcomes. We will train research and lab staff regarding each related steps and data collection. We have pilot tested assessments. The data collection will be supervised and assessed regularly for discrepancies.

Plans to promote participant retention and complete follow-up {18b}

We have planned to send daily reminders to participants to use their assigned mouthwashes and follow-up the next day to see if they have used it and if there were problems.

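### Language stratifies the randomisation but is missing from the proportional hazards models; if it is related to Ct, the hazard ratio is attenuated and some power is lost

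*Combined protocol and SAP*

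**What the plan says.** Sequence generation {16a} makes language the only stratification factor: "The permuted block allocation sequence stratified on language (English/Spanish) will be generated in SAS and uploaded to REDCap". The block size is not given.

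Statistical methods {20a} compares each active group with water on Ct using "proportional hazards regression models with right censoring for undetermined Ct, stratifying on replicate for a marginal repeated measures survival model". Replicate is the only stratum, and no covariate is named.

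Methods for additional analyses {20b} carries the same form to the other time points: "Similar proportional hazards regression analyses will be conducted for baseline (after rinse) and day 7". It then adds: "We will assess the relationship between study results and baseline variables (demographics, clinical symptoms, tobacco use, etc". That sentence describes a separate look at baseline variables. It does not name language and does not place it in the arm comparison.

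Sample size {14} plans on "a sample size of 24 for a mouthwash group and 24 for the distilled water control group", with "80% power to detect a 2-fold difference in mean values between the 2 groups with a 2-sided alpha=0.05".

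**The concern.** Blocking on language balances the arms within English and Spanish speakers. An analysis that ignores the blocking factor does not use that balance. If language predicts Ct, two things follow in a proportional hazards model:

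- The hazard ratio averaged over language lies closer to 1 than the hazard ratio within language.
- The test gives up power, because the language differences remain as unexplained variation.

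The trial is a pilot whose stated purpose is to estimate effect sizes for a later definitive trial, with about 24 evaluable participants per group. An attenuated estimate and an avoidable loss of power both work against that purpose. The stratum is known for every participant at randomisation.

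**Working it through.** **The plan's own figures.** From {14}, 24 / 0.80 = 30 per group and 5 x 30 = 150, as stated. The 24 cannot be checked because no SD is given. Solving 24 = 2 x (1.96 + 0.84)^2 x SD^2 / (ln 2)^2 gives an SD of about 0.86 on the natural-log scale. The stated 80% power is taken as given for the linear check.

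**Assumptions.** The documents give neither the Spanish-speaking share q nor the language difference in Ct, d (in within-language SDs). I use q = 0.20-0.35 and d = 0.3-0.8. I read a marginal repeated-measures model as implying a cluster-robust variance, which {20a} does not name.

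**Linear approximation.** Let v = q(1-q)d^2 and k = sqrt(1+v). With balance within language, the true SE of the arm difference is smaller than the unadjusted SE by the factor k. Then:

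- size without language = 2(1 - Phi(1.96k))
- power without language = Phi((2.80 - 1.96)k)
- power with language = Phi(2.80k - 1.96)

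| q | d | v | k | Size without | Power without | Power with | Gain (points) |
|---|---|---|---|---|---|---|---|
| 0.20 | 0.3 | 0.0144 | 1.0072 | 4.8% | 80.1% | 80.5% | 0.4 |
| 0.35 | 0.8 | 0.1456 | 1.0703 | 3.6% | 81.6% | 85.0% | 3.4 |

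With 2.8016 in place of 2.80, the low-end powers become 80.2% and 80.6%; the gains are unchanged at 0.4 and 3.4. With d = 0, k = 1 and there is no gain.

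**The planned type of model.** This was simulated with 24 versus 24, near-complete balance within language, two replicates (correlation 0.95), a cluster-robust Cox model, no censoring and 1,500 runs per setting. Each pair reads replicate strata only / replicate x language strata. The log hazard ratio and power columns are for a within-language hazard ratio of 2 (log 0.693).

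| q | d | Reported/true SE, replicate only, null | Null rejection | Mean log hazard ratio | Power |
|---|---|---|---|---|---|
| 0.25 | 0.5 | 0.98 | 5.5% / 6.9% | 0.69 / 0.72 | 62% / 66% |
| 0.25 | 1.0 | 1.01 | 5.3% / 7.1% | 0.62 / 0.71 | 56% / 66% |
| 0.50 | 1.0 | 1.11 | 3.5% / 6.9% | 0.55 / 0.71 | 45% / 64% |

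- The Monte Carlo error is about sqrt(0.05 x 0.95 / 1500) = 0.6 points for size and sqrt(0.62 x 0.38 / 1500) = 1.3 points for power.
- Power starts below 80% because a Cox comparison at hazard ratio 2 with 48 events has about Phi(0.693 x sqrt(48/4) - 1.96) = 67%.
- Adding language hardly changes the reported SE (about 0.287 versus 0.286 at q = 0.25). The gain comes mainly from removing attenuation.
- At d = 0 the reported/true SE ratio is already 0.93. The robust variance is too small at this sample size whether or not language matters.
- Part of the simulated power gain reflects the raised null rejection after adding language, so these differences are upper readings.
- With 40% censoring the SE ratio without language is 1.00-1.02 at d = 0.5 and 1.05-1.12 at d = 1. At d = 1, q = 0.5, null rejection is 2.6% without language and 5.3% with it.

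A second simulation used five-arm permuted blocks of 5, 150 enrolled and 80% random retention. Without language, the SE ratio was 0.93-1.00 and null rejection 4.2-7.0% at d = 0.3; at d = 0.8 they were 0.99-1.05 and 3.5-4.8%. Adding language as a covariate without a variance correction gave null rejection of 6.2-7.9% uncensored and 4.6-5.8% with 40% censoring.

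**The case against.** The strongest reply is that nothing in the documents links language to Ct. Eligibility already requires a positive sample from the prior 7 days, the primary comparison is at day 28, and this is a pilot in which a conservative test does little harm. This stands as a limit on size: with a weak link the effect is a fraction of a power point.

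It can also be said that the unadjusted hazard ratio is a legitimate population-average quantity, so attenuation is not bias in the strict sense. That is fair. The loss of power remains, because the estimate shrinks while its standard error barely moves.

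The baseline-variable sentence in {20b} might be offered as covering the gap. It does not: it adds a separate analysis and leaves the arm comparison unchanged.

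Three stronger readings are tempting, and the material does not support them:

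- **Standard errors are too large throughout.** That is a linear-model result. In a marginal Cox model at about 24 per arm, the small-sample bias of the robust variance runs the other way, and the reported/true ratio at d = 0.5 is only about 0.98-1.02.
- **Adjusting lifts power from 80% to as much as 85%, worth 1.4-15% more participants (k^2 - 1).** That takes simple randomisation as its starting point. Under the stratified design, power without language is already 80.1-81.6%.
- **Adjusting has no downside.** With an uncorrected robust variance, both simulations show null rejection above 5% in several settings.

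**Conclusion.** The mismatch between design and analysis is real: the sole randomisation stratum is absent from the primary, after-rinse and day-7 models, with no reason given. The consequence is conditional. If language is related to Ct, the hazard ratio is attenuated toward 1 and some power is lost. The test becomes conservative only when the link is strong, and the omission does not itself inflate type I error.

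Under the assumed ranges the linear approximation gives a loss of about 0.4 to 3.4 power points. Cox attenuation can make it larger, with the big simulated differences arising at d = 1, outside the 0.3-0.8 range. This is an efficiency point worth fixing because the change is cheap; it does not threaten the validity of the trial.

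**What to change.** In {20a} and {20b}, include language in every active-versus-water model, either as a covariate or by stratifying on replicate x language, and say that the reported hazard ratio is then conditional on language. Name the cluster-robust variance and specify a small-sample correction to it. Settle this before the interim analysis in {21b}, which has only 10 completers per group, so that the choice cannot look data-driven. If the sponsor prefers to leave language out, state why.

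The cost is a short addition to the analysis text and about one degree of freedom. Without the variance correction there is also slight type I inflation at about 24 per arm. Sample size, data collection and trial conduct do not change.
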